6.3.5 Secondary Efficacy Endpoints

6.3.5.1 S01: Penn Facial Pain Scale-Revised (Penn-FPS-R)

The Penn-FPS-R is a 12-item scale used to assess the impact of TN pain on health-related quality of life and activities of daily living. Developers of the original Penn-FPS-R applied standard validation metrics (e.g., concept elicitation, cognitive debrief, reliability, responsiveness) to the Penn-FPS-R as a measure for use in assessing treatment impacts on TN symptoms. The response categories for each of the 12 items range from 0 ('does not interfere') to 10 ('completely interferes'). The specified recall period is for the 'past week.' Anchors to scale 0 to 10 were added by the Sponsor.

Subjects are asked to complete the Penn-FPS-R at the beginning and end of each treatment phase, as outlined in the Schedule of Assessments.

Change from baseline in Penn-FPS-R total score will be analyzed using the same methodology as the primary endpoint (see Section 6.3.4.1) with baseline total score as the covariate.

6.3.5.2 S02: Pain Disability Index

The Pain Disability Index is designed to measure the degree to which a patient's daily life is disrupted by their pain. The seven items of the scale reflect different "life activities" and are scored on an 11-point Likert Scale, with "0" representing "no disability" and "10" representing "worst disability."

Subjects are asked to complete the Pain Disability Index at the beginning and end of each treatment phase, as outlined in the Schedule of Assessments.

Change from baseline in Pain Disability Index total score will be analyzed using the same methodology as the primary endpoint (see Section 6.3.4.1) with baseline index as the covariate.

6.3.5.3 S03: Patient Global Impression of Change Scale (PGI-C)

The PGI-C is a patient-rated scale which assesses how the subject's current illness state has improved or worsened relative to the baseline visit. The subject is asked to rate a change in their overall disease condition on a 7-point scale, from 1 ('no change') to 7 ('a great deal better'). The PGI-C is a global index scale that may be used to rate the response of a condition to a therapy.

The PGI-C will be conducted at the beginning and end of each treatment phase as indicated in the Schedule of Assessments.

The PGI-C will be analyzed using the method specified in Section 6.3.2. The MMRM table has the same format as the one described in Section 6.3.2.

6.3.5.4 *S04: Worst Pain Episode*

Using the 11-point NPRS described above, subjects are asked to record an intensity rating of their worst pain episode over a 24-hour period daily in their paper diary.

Worst pain episode score will be analyzed using the same methodology as the primary endpoint (see Section 6.3.4.1) with baseline score as covariate.

6.3.5.5 *S05: ≥ 2 -Point Reduction in the 11 Point NPRS*

Achievement of ≥ 2 -point reduction in average NPRS score will be analyzed using logistic regression, that will include terms for treatment group, randomization strata (typical/atypical), sequence, and baseline NPRS score. See Section 6.3.3 for details. The regression table has the same format as the one described in Section 6.3.3.

6.4 Safety Analyses

Safety outcome measures include: AEs, laboratory assessments, vital signs, ECGs, concomitant medications, and the S-STS questionnaire.

Tables of safety endpoints are provided according to safety analysis period and analysis set as follows, unless otherwise noted:

- On-DBT for the DBT treated analysis set by treatment sequence and period, rimegepant pooled, and placebo pooled
- Post-DBT pre-OL rimegepant for the interim treated analysis set by treatment sequence and period, rimegepant pooled, placebo pooled, and overall
- On-OL rimegepant for the OL rimegepant treated analysis set by DB rimegepant pooled/OL rimegepant, DB placebo pooled/OL rimegepant, and overall. Shifts from baseline are based on the OL rimegepant baseline.
- On-DB or OL rimegepant for the DB or OL rimegepant treated analysis set by DB rimegepant pooled/OL rimegepant, DB placebo pooled/OL rimegepant, and overall. Shifts from baseline are based on the DB or OL rimegepant baseline.
- Follow-up for the follow-up treated analysis set by DB rimegepant pooled/OL rimegepant, DB placebo pooled/OL rimegepant, and overall.

6.4.1 *Adverse Events*

Refer to the Core SAP for the following: AE start and end date imputation; death date derivation; rules for counting and rounding in frequency tables; definitions of treatment-emergent adverse events (TEAEs), AEs related to study drug, and exposure-adjusted multiple occurrences of unique AEs; and TLF contents.

A by-subject AE listing is provided for the enrolled analysis set. TEAEs are identified.

6.4.1.1 *Deaths*

Deaths are identified from any of the following sources:

- AE CRF with any of the following: PT or reported term of “death”; outcome of fatal; “yes” response to any death-related question (e.g., “Did the SAE result in death?”; “Is a

death certificate available?"; "Is an autopsy report available?"); complete or partially complete death date

- Study Termination Summary CRF with any of the following: death as reason for discontinuation; complete or partially complete death date

The by-subject listing of deaths is provided for the enrolled analysis set.

6.4.1.2 AE Overviews

An AE overview frequency table displays the following categories without SOC and PT: any AE; mild AE; moderate AE; severe AE; moderate or severe AE; AE related to study drug; AE leading to study drug discontinuation; SAE; SAE leading to study drug discontinuation; hepatic-related AE; cardiovascular AE; and suicidality AE.

AE overview tables are produced for the following safety analysis periods and analysis sets:

- Pretreatment for the DBT treated analysis set
- On-DBT for the DBT treated analysis set
- Post-DBT pre-OL rimegepant for the interim treated analysis set
- On-OL rimegepant for the OL rimegepant treated analysis set
- On-DB or OL rimegepant for the DB or OL rimegepant treated analysis set
- Follow-up for the follow-up treated analysis set.

6.4.1.3 On-DBT AEs

Frequency tables of on-DBT AEs are provided for the DBT treated analysis set by SOC and PT for the following endpoints:

- AEs by intensity
- AEs related to study drug by intensity
- AEs by relationship to study drug (related, possibly related, unlikely related, not related, not reported)
- SAEs
- AEs leading to study drug discontinuation
- Exposure-adjusted multiple occurrences of unique AEs
- Hepatic-related AEs by intensity *
- Cardiovascular AEs *
- Suicidality AEs *.

AEs of special interest are asterisked ("*").

AEs with a start date on or after the first dose date/time on the Day 1 visit and prior to the first dose date/time on the Day 21 visit is considered to be in the on-DBT analysis period 1. AEs with a start date on or after the first dose date/time on the Day 21 visit to the earlier of the last dose of the DBT + 7 or the first dose of OLE - 1 is considered to be in the on-DBT analysis period 2.

Calculations for on-DB rimegepant exposure-adjusted multiple occurrences of unique AEs use an analysis period reference start date = DB rimegepant start date, analysis period reference end date = DB rimegepant last date + 7 days.

6.4.1.4 *On-OL Rimegepant AEs*

Frequency tables of on-OL rimegepant AEs are provided for the OL rimegepant treated analysis set by SOC and PT for the following endpoints:

- AEs by intensity
- AEs related to study drug by intensity
- AEs by relationship to study drug (related, possibly related, unlikely related, not related, not reported)
- SAEs
- AEs leading to study drug discontinuation

AEs with a start date on or after the first dose date/time of OL rimegepant and prior to the last dose date of the OL rimegepant + 7 is considered to be in the on-OL analysis period.

6.4.1.5 *On-DB or OL Rimegepant AEs*

On-DB or OL rimegepant AEs are provided for the DB or OL rimegepant treated analysis set by SOC and PT for the same endpoints listed in Section [6.4.1.3](#).

AEs with a start date on or after the first dose date/time of DB rimegepant or OL rimegepant and prior to the last dose date of the DB or OL rimegepant + 7 is considered to be in the on-DB or OL rimegepant analysis period.

Calculations for on-DB or on-OL rimegepant exposure-adjusted multiple occurrences of unique AEs use an analysis period reference start date = DB or OL rimegepant start date, analysis period reference end date = DB or OL rimegepant last date + 7 days.

6.4.1.6 *Post-DBT Pre-OL Rimegepant AEs*

Frequency tables of post-DBT pre-OL rimegepant AEs are provided for the interim treated analysis set by SOC and PT for the following endpoints:

- AEs by intensity
- SAEs
- AEs leading to study drug discontinuation.

AEs with a start date after the last dose date/time of DB + 7 and before the OL rimegepant start date is considered to be in the post-DB Pre-OL rimegepant analysis period.

6.4.1.7 *Follow-up AEs*

Frequency tables of follow-up AEs are provided by SOC and PT for the follow-up treated analysis set for the following endpoints:

- AEs by intensity

- SAEs.

For subjects who did not continue into the OL rimegepant period, AEs with a start date after the last dose date/time of DB + 7 is considered to be in the follow-up analysis period. For subjects who continued into the OL rimegepant period, AEs with a start date after the last dose date/time of OL rimegepant + 7 days is considered to be in the follow-up analysis period.

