3.2 Estimands

An estimand is the target of estimation to address the scientific question of interest posed by a study objective. The 4 attributes of an estimand include the population of interest, endpoint of interest, specification of how intercurrent events are reflected in the scientific question of interest, and the summary for the endpoint.

For all objectives, the population of interest is defined through appropriate inclusion/exclusion criteria to reflect the targeted patient population for approval. Refer to the protocol for inclusion/exclusion criteria.

Intercurrent Events

Intercurrent events are those that occur after treatment initiation and either preclude observation of the endpoint or affect its interpretation. The following will be considered intercurrent events:

- Study drug discontinuation before the time point of interest defining the endpoint.
 - For safety objectives:
 - For AEs, study drug discontinuation is handled with a “while-on-treatment strategy,” i.e., response to treatment prior to the occurrence of the intercurrent event of interest, such that all observed values of the endpoint of interest will be used prior to study drug discontinuation.
 - For all other safety endpoints, study drug discontinuation is handled with a “treatment policy strategy”, i.e., the occurrence of the intercurrent event will be considered irrelevant, such that all observed values of the endpoint of interest will be used regardless of study drug discontinuation.
 - For efficacy objectives:
 - For the NPRS objectives, study drug discontinuation is handled with a “while-on-treatment strategy”.
 - For the Penn-FPS-R, PDI, and PGI-C efficacy objectives, study drug discontinuation is handled with a “treatment policy strategy”.
 - For all other objectives (i.e., use of non-study TN standard of care medications on or before the time point of interest), this intercurrent event will be handled with a “while-on-treatment strategy”

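### SAP AE windows: on-DBT period 1 has no stated end for patients who stop before the Day 21 dose, and day +7 after the last open-label dose falls in no period

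*SAP*

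**What the plan says.** SAP 7.2 sets no AE windows of its own and refers back to 6.4.1, where they are defined.

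- **On-DBT period 1 (6.4.1.3):** from the first dose on Day 1. AEs starting "prior to the first dose date/time on the Day 21 visit is considered to be in the on-DBT analysis period 1".
- **On-DBT period 2 (6.4.1.3):** from the first dose at the Day 21 visit "to the earlier of the last dose of the DBT + 7 or the first dose of OLE - 1".
- **On-OL (6.4.1.4):** from the first open-label dose. AEs starting "prior to the last dose date of the OL rimegepant + 7 is considered to be in the on-OL analysis period".
- **On-DB or OL rimegepant (6.4.1.5):** from the first rimegepant dose, "prior to the last dose date of the DB or OL rimegepant + 7". The exposure-adjusted calculation in the same section uses the last rimegepant date + 7 days as its reference end.
- **Post-DBT pre-OL (6.4.1.6):** after last DB dose + 7 and before the open-label start.
- **Follow-up (6.4.1.7):** "For subjects who did not continue into the OL rimegepant period, AEs with a start date after the last dose date/time of DB + 7" are in follow-up. For those who did continue, "AEs with a start date after the last dose date/time of OL rimegepant + 7 days is considered to be in the follow-up analysis period".

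For AEs, SAP 3.2 names a while-on-treatment strategy, "such that all observed values of the endpoint of interest will be used prior to study drug discontinuation".

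**The concern.** The period 1 end and the period 2 start both rest on a dose that an early stopper never takes. Such patients are foreseen: SAP 6.2.3.1 tabulates withdrawals from the first treatment period, and the sample size allows for 20% dropout. Period 2 carries a limit of last dose + 7, and period 1 carries none.

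At the end of the extension, one rule stops short of last dose + 7 and the next begins beyond it. The protocol's schedule footnotes have non-serious AEs reported through the safety follow-up visit, nominally 14 days after the end-of-treatment visit. Day +7 is therefore a day on which AEs are collected.

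At stake is which table an AE enters. A late AE in an early stopper could appear as both on-treatment and follow-up, and an AE on day +7 of the extension could appear in neither. The frequency tables would then depend on a programmer's guess.

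**Working it through.** No power or sample size figure is involved. The check is to apply the written windows, at date level, to example patients. Let L be the day of the last dose in the relevant phase. Day 1 is the first dose, and the Day 21 visit is taken to fall on Day 21.

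**Boundary rules side by side**

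| Window | Upper or lower limit at last dose + 7 |
|---|---|
| On-DBT period 1 | none; ends only at the Day 21 dose |
| On-DBT period 2 | AE day ≤ L + 7, or ≤ first OLE day − 1 if earlier (*to*, read as inclusive) |
| Interim, or follow-up without OLE | AE day > L + 7 |
| On-OL | AE day < L + 7 |
| Follow-up after OLE | AE day > L + 7 |

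Period 2 (≤) meets interim or follow-up (>) with nothing between. On-OL (<) and follow-up (>) leave AE day = L + 7 unassigned.

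**Four example patients**

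1. *Completer, no OLE, last dose Day 35.* 35 + 7 = 42. Period 1 is Days 1–20, period 2 is Days 21–42, and follow-up starts on Day 43. No gap.
2. *Completer, OLE Days 36–119.* Period 2 ends at min(42, 36 − 1) = Day 35. 119 + 7 = 126, so on-OL is Days 36–125 and follow-up starts on Day 127. **Day 126 is in no period.**
3. *Completer who returns later, OLE taken as Days 200–283 for illustration.* Interim is Days 43–199. 283 + 7 = 290, so on-OL is Days 200–289 and follow-up starts on Day 291. **Day 290 is in no period.**
4. *Stops on Day 10.* 10 + 7 = 17, so follow-up starts on Day 18. Period 1 starts on Day 1 and has no end. Read as open-ended, Days 1–17 are period 1 only, and **every day from Day 18 is both period 1 and follow-up.** If the follow-up visit falls 14 days after the last dose (Day 24), the overlap is Days 18–24, or 7 days.

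**DB-or-OL window.** For patient 2 it ends with Day 125, while the exposure-adjusted reference end is Day 126. Within 6.4.1.5 the event rule and the reference period differ by one day.

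**Size.** Planned dropouts are 20% × 60 = 12. Their timing is not given, so between 0 and 12 might stop before the Day 21 dose. The extension gap is one day per OLE patient. Days 36–119 are 84 days and nominal follow-up adds 14, so the gap is 1 of 98 days, about 1%. If clock times are compared, it shrinks to the part of that day up to the time of dosing.

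**The case against.** The strongest reply is that the intent is clear. Section 6.4.1.7 starts follow-up after last DB dose + 7, which implies where on-DBT ends. SAP section 1 gives the Core SAP primacy where this SAP is silent, and 6.4.1 takes the definition of treatment-emergent AEs from it. On-DBT and follow-up AEs go into separate tables, and AE tables count a subject once per event. This partly stands. The Core SAP is not available, so a fallback for early stoppers can be neither confirmed nor excluded. An implied end is still not a stated one, and the on-OL limit is not a silence but a rule that this SAP states itself.

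A reader might infer more than the documents support:

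- *That early stoppers' AEs are dropped from the on-DBT tables.* This would follow only if the code treated a comparison with a missing date as false. No code is in the documents.
- *That early stoppers have no on-treatment window at all.* A rimegepant-first patient keeps the 6.4.1.5 window and the exposure-adjusted window in 6.4.1.3 ("reference end date = DB rimegepant last date + 7 days"). Neither needs a Day 21 dose. A placebo-first early stopper has neither.
- *That AEs leading to discontinuation are put at risk.* The overlap and the gap both lie a week or more after the last dose, and an AE that led to stopping would ordinarily start earlier. Section 6.4.1.8 also tabulates these AEs across all periods combined.
- *That the hole affects the randomized comparison.* It arises at the end of the single-treatment extension. For a completer who does not enter OLE, day +7 after a last rimegepant dose in period 2 lies in on-DBT period 2.
- *That SAP 3.2 sets a competing window.* Section 7.2 ties the while-on-treatment strategy for AEs to the 6.4.1 windows, so the difference is one of wording.

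**Conclusion.** Two defects stand. On-DBT period 1 has no stated end for a patient who never takes the Day 21 dose, and read as open-ended it overlaps follow-up from day +8. For OLE patients, an AE starting on day +7 after the last open-label dose is in neither the on-OL nor the follow-up period. The DB-or-OL window has the same exclusive end and disagrees by one day with its own reference end.

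The effect is small and confined to descriptive safety tables. The range of 0 to 12 early stoppers uses the planned 60 patients and makes no assumption about when they stop. SAP section 1 says the study was terminated early for low enrollment, so the real number may be zero. No count of OLE patients is given either. The by-subject AE listing covers all enrolled patients, so no event is lost from the record. The date-level results read *to* as inclusive in period 2 and *prior to* and *after* as exclusive.

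**What to change.** - **6.4.1.3:** keep the present date/time boundary at the first Day 21 dose and add *or, if no such dose was taken, through last DBT dose + 7 days*. Closing period 1 on the day before that dose may look tidier, but an AE starting on Day 21 before dosing would then be in neither period.
- **6.4.1.4 and 6.4.1.5:** replace *prior to* with *on or before* last dose date + 7, and state that dates, not clock times, are compared. Apply the same date-level comparison to the follow-up start in 6.4.1.7, so that follow-up begins on day +8.
- **3.2 (optional, editorial):** say that the while-on-treatment strategy for AEs uses the 6.4.1 windows.

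Check of the revised rules: a stop on Day 10 gives period 1 on Days 1–17 and follow-up from Day 18, with no overlap. A last OLE dose on Day 119 gives on-OL on Days 36–126 and follow-up from Day 127, with no gap.

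The cost is three amended sentences, the note on date-level comparison and the matching derivation code. No new data are needed.

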- Total OL rimegepant exposure (tablets) summed across all subjects, derived by summing cumulative OL rimegepant exposure across all subjects
- Total OL rimegepant exposure (patient-years), derived by summing (OL rimegepant end date – OL rimegepant start date + 1)/365.25 across all subjects.

DB or OL Rimegepant Exposure

DB or OL rimegepant exposure will be summarized descriptively by as-treated DB rimegepant pooled/OL rimegepant, DB placebo pooled/OL rimegepant and overall, and will include the following parameters:

- Time on DB or OL rimegepant (days), derived as DB or OL rimegepant end date – DB or OL rimegepant start date + 1
- Time on DB or OL study drug category (weeks)
- Cumulative DB or OL rimegepant exposure (mg), derived by summing number of DB or OL mg across records with non-missing DB or OL rimegepant date/times.
- Average DB or OL rimegepant exposure (mg per day), derived as cumulative DB or OL rimegepant exposure/time on DB or OL rimegepant.

- Total DB or OL rimegepant exposure (tablets) summed across all subjects, derived by summing cumulative DB or OL rimegepant exposure across all subjects. Total DB or OL rimegepant exposure includes missed dose days within a study phase and excludes the dosing break between study phases (i.e., (last dose day of DB study drug – first dose date of DB study drug + 1) – (number of days with a dosing break between the DB and OL phases)).
- Total DB or OL rimegepant exposure (patient-years), derived by summing (DB or OL rimegepant end date – DB or OL rimegepant start date + 1)/365.25 across all subjects.

A by-subject listing of study drug exposure will be provided for the treated analysis set.

6.2.6.2 *Drug Accountability and Compliance*

DB study drug accountability and compliance will be tabulated by as-treated treatment groups for period 1 placebo, period 1 rimegepant, period 2 rimegepant, period 2 placebo, rimegepant pooled, placebo pooled, and overall with the number and percentage of subjects in the following categories for the DB phase:

- Any bottle dispensed (Yes, No, Not Reported)
- DB study drug taken but not randomized
- Tablet count compliance < 80% from study drug start to study drug end in DB phase
- More than the required number of tablets administered on 1 day
- Did not return ≥ 1 bottle dispensed and discontinued study drug, defined as any of the following:
 - Randomized subjects who were not treated and did not return DB bottle dispensed

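### Combined double-blind or open-label rimegepant time and AE window run over a single span, so a rimegepant-first OLE patient's placebo days count as rimegepant, and the rule for the break between phases conflicts with the formulas

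*SAP*

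**What the plan says.** SAP 6.2.6.1 has a block for combined double-blind (DB) or open-label (OL) rimegepant exposure.

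- Time: "Time on DB or OL rimegepant (days), derived as DB or OL rimegepant end date" minus the corresponding start date, plus 1.
- Average mg/day: "derived as cumulative DB or OL rimegepant exposure/time on DB or OL rimegepant".
- Patient-years: "Total DB or OL rimegepant exposure (patient-years), derived by summing" the same span divided by 365.25.
- The tablets bullet adds that total exposure "includes missed dose days within a study phase and excludes the dosing break between study phases". Its formula takes the last minus the first dose date of DB study drug, plus 1, and subtracts the "number of days with a dosing break between the DB and OL phases".

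SAP 6.4.1.5 sets the combined AE window as a "start date on or after the first dose date/time of DB rimegepant or OL rimegepant and prior to the last dose date" plus 7. For exposure-adjusted AEs it gives one pair of reference dates, with "analysis period reference end date = DB or OL rimegepant last date + 7 days".

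SAP 6.4.1.3 assigns an AE to on-DBT period 2 when its onset falls "on or after the first dose date/time on the Day 21 visit to the earlier of the last dose of the DBT + 7", the other possible end being the day before the first OLE dose. Earlier AEs belong to period 1. SAP 6.4.1.6 gives AEs in the gap between phases their own interim period.

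**The concern.** A single first-to-last span works when a patient stays on one drug. Here a rimegepant-first patient who enters the OLE takes rimegepant, then placebo, then rimegepant again, and none of the printed formulas removes the placebo stretch. Three things follow.

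- Time, patient-years and average mg/day are wrong for that patient even with perfect compliance.
- An AE starting in placebo period 2 is counted under placebo in the on-DBT tables and under rimegepant in the combined tables.
- Protocol 3.4 and 4.1 let patients who finished the double-blind phase before the OLE was added come back for it. For them, in both sequences, the span also covers the off-drug break. The SAP says total exposure excludes that break, but neither the time nor the patient-years formula subtracts it.

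These are the outputs that describe rimegepant safety over all exposure in this trial. The wider window can add patients to the any-AE and preferred-term counts. The longer denominator lowers mg/day and would dilute any rate based on it.

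**Working it through.** The documents state no combined exposure total, so there is no figure of theirs to reproduce. The schedule itself is consistent: 14 + 7 + 14 = 35 double-blind days, and 119 − 36 + 1 = 84 OLE days = 12 weeks.

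**Inputs.** Two 2-week periods with a 7-day placebo washout (Protocol 3.5.2, SAP 2.1); OLE on Days 36 to 119, first dose on Day 36 (Protocol 3.5.3, 3.5.4); 75 mg once daily, no dose adjustments (Protocol 6.2.2, 6.2.3). Nominal days: period 1 = 1–14, washout = 15–21, period 2 = 22–35, OLE = 36–119.

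**Time and average dose, no break, OLE completed, fully compliant**
- Rimegepant actually taken: 14 + 84 = 98 days in either sequence; 98 × 75 = 7350 mg.
- Printed, rimegepant-first: 119 − 1 + 1 = 119 days. Excess 21 days; 119/98 = 1.214. Average 7350/119 = 61.8 mg/day, against 7350/98 = 75.
- Printed, placebo-first: 119 − 22 + 1 = 98 days, no error.
- If the washout starts at the Day 14 visit, the rimegepant-first excess is 22 days over 97 (22.7%).

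**Pooled patient-years, equal sequences**
- All 60 enter and complete the OLE: printed 30 × (119 + 98)/365.25 = 17.82; correct 30 × (98 + 98)/365.25 = 16.10; +10.7%.
- The documents do not give the OLE fraction p. If p is the same in both sequences and everyone else contributes 14 days, the excess is 10.5p/[98p + 14(1 − p)]: 10.7% at p = 1, 10.2% at 0.75, 9.4% at 0.5, 7.5% at 0.25.

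**AE window, rimegepant-first**
- SAP 6.4.1.3 ends the DB rimegepant reference period at last dose + 7, nominally Day 14 + 7 = Day 21. The washout is therefore already covered by the SAP's own rule.
- End day included: printed Days 1–126 = 126. Union of Days 1–21 and 36–126 = 21 + 91 = 112. Excess 14.
- Window ending before last dose + 7, as the AE sentence has it: printed Days 1–125 = 125. Union 21 + 90 = 111. Excess 14.
- Either way the excess is Days 22–35, which is placebo period 2 for this sequence.

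**Break of g days before the OLE**
- Printed time is 119 + g (rimegepant-first) or 98 + g (placebo-first), against 98. The number of returners and the length of their breaks are not stated. For assumed breaks of 30 to 365 days this gives 149 to 484 or 128 to 463.
- The printed exclusion formula gives 35 − g. With no break that is 35 days, so all 84 OLE days are missing.
- If its DB study drug dates are read as DB or OL rimegepant dates, a rimegepant-first patient gets (119 + g) − g = 119. The break goes, but the 21 placebo days stay.

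**The case against.** The strongest reply is that the SAP never says earliest or latest. The start and end dates could be read phase by phase, or the AE sentence as the union of two windows. That may be the intention, but neither reading is printed, and one pair of reference dates with a plain end-minus-start formula points the other way. A programmer following the text would compute one span.

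The Core SAP is a fair point. A reader might infer that it cannot alter any of this, because SAP 1 gives the study SAP primacy. But SAP 1 also gives the Core SAP primacy where it is directly referenced, and SAP 6.4.1 refers to it for the definition of exposure-adjusted AEs. It was not available, so the effect on that one table is less certain. The time, patient-years and AE-window dates are printed in the study SAP itself.

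Materiality is limited. The trial stopped early, SAP 1 says only critical data will be analyzed, and no significance is evaluated (SAP 5). The AEs also remain visible by sequence and period in the on-DBT tables. Still, SAP 8 includes all described analyses. ECG, COVID-19 impact and pharmacokinetics are dropped explicitly; the combined tables are not.

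Four stronger readings are not supported:
- That all 21 placebo days, or 15 of them, are misassigned in the AE window. Days 15–21 fall within the printed last dose + 7, which leaves 14.
- That every combined rimegepant percentage can only rise. This holds for any-AE and preferred-term counts. Within intensity rows a patient may move to a higher grade, because only the greatest intensity is reported (Protocol 9.4.6).
- That the SAP intends negative exposure after a long break. The exclusion formula goes negative when g exceeds 35, but this looks like a drafting slip, and its missing OL days already show that it needs replacing.
- That the column problem described under the fix applies equally to the combined and follow-up tables. Those can include patients who stopped during the double-blind phase, so their two columns need not match.

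**Conclusion.** The combined exposure and AE definitions are wrong as written for this crossover and should be corrected. For a rimegepant-first patient with no break who completes the OLE, time is overstated by 21 days (+21%), average dose is understated at 61.8 against 75 mg/day, and 14 days of placebo period 2 enter the on-rimegepant AE window. These figures rest on nominal days and full compliance. The pooled overstatement of about 10.7% also assumes that everyone enters and completes the OLE, with equal sequences.

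The break rule conflicts with the time and patient-years formulas, and its own formula omits the OL days. How much this matters depends on how many patients returned and after how long, which the documents do not state.

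The damage stays within the combined descriptive safety and exposure outputs. Efficacy, the on-DBT tables, OL-only exposure and cumulative mg are not affected.

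**What to change.** - Define combined time on rimegepant and patient-years as the DB rimegepant interval plus the OL rimegepant interval. Average mg/day then corrects itself.
- Define the combined AE window and the exposure-adjusted reference period as the union of two windows: DB rimegepant start to last dose + 7 days, and OL start to last dose + 7 days. Count overlapping days once and use one convention for whether the seventh day is included. Check this against the Core SAP definition of exposure-adjusted AEs.
- Replace the break sentence and its DB-only formula with one rule that applies to all combined measures, and move it out of the tablets bullet.
- Secondary: patients who discontinue the double-blind phase early cannot enter the OLE (Protocol 5.4), so OLE entrants have received both treatments. In the on-OL tables, the columns for DB rimegepant pooled followed by OL and DB placebo pooled followed by OL therefore hold the same people. Present these tables by treatment sequence, as SAP 6.2.6.1 already does for OL exposure.

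The cost is SAP wording and derivation code. The dosing dates are already collected.
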